## V. Monitoring

### 5.1 Data monitoring

Data collection (including observational, adolescent girl, and principal/science teacher/HEW data collection) will be undertaken using electronic tablets. Checks will be built into the CAPI software and applied at the time of data entry. These will include logic checks, valid values, skip patterns, and range checks among others to ensure efficiency and high data quality. In addition, enumerator monitoring will be incorporated into the CAPI software including recording the duration of interviews and GPS location of enumerators during data collection.

Field supervisors, project manager, and principal and co-principal investigators of the survey firm and IFPRI will closely monitor enumerators and the quality of data collected to ensure the integrity of the data during data collection.

### 5.2 Harms

The nutrition interventions will primarily focus on behavior change related to healthy diets, and we do not anticipate any harms from the study. Any adverse events or unintended effects during provision of interventions will be recorded and monitored, and subjects will be referred to their nearest health provider as appropriate.

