## 2.3 Interventions

The package of locally tailored adolescent nutrition interventions will include in-school education about nutrition and healthy food choices, mentoring and peer group activities related to nutrition, and parent education on adolescent nutrition during school and community meetings. Intervention components are presented in **Table 2**.

Table 2. Description of interventions for treatment and control primary schools

CORE INTERVENTIONS	INTERVENTION PRIMARY SCHOOLS	CONTROL PRIMARY SCHOOLS
At school:		

 
Classroom education about healthy diet and nutrition
 
	Classroom lessons related to nutrition, dietary diversity, healthy food choices and hand washing	Standard health education

 
Flag events or assemblies about healthy diet and nutrition
 
	Flag events or school assemblies led by principals to provide messages on nutrition, dietary diversity, healthy food choices and hand washing	Standard flag ceremonies or assemblies

 
Peer group mentoring on healthy diets and nutrition
 
	Selected adolescent girls are mentored by science teachers as peer mentors and hold weekly group discussions with other girls to discuss nutrition, dietary diversity, healthy food choices and handwashing	None

 
BMI measurement and counseling
 
	Trained science teachers take anthropometric measurements of adolescent girls to calculate BMI and provide nutrition counseling	None
Parent-teacher meetings	Parent-teacher meetings to inform and encourage parents about adolescent nutrition, dietary diversity, healthy snacks, and handwashing	Parent-teacher associations focused on school performance and management
Home visits by health workers	Home visits by HEWs and/or community volunteers to discuss with parents about adolescent nutrition, dietary diversity, i healthy food choices, and handwashing	Home visits for routine health services
Community gatherings to discuss adolescent nutrition	Community gatherings by HEWs and meetings with religious leaders to discuss with parents about adolescent nutrition, dietary diversity, healthy food choices, and handwashing	None
Training for school staff and other actors	Workshop on the adolescent nutrition interventions above for school principals, science teachers, HEWs, supervisors, and woreda officers	Standard education training

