#### 4.1.4 Adolescent girl questionnaire

Interviews with adolescent girls will be conducted at baseline and endline and gather information on school attendance, exposure to nutrition information, dietary diversity, meal and snacking habits, WASH practices, health and health seeking behaviors, health and nutrition knowledge, food security, home food environment, parental interactions, social desirability, gender and marriage beliefs and decision-making power, and anthropometry.

Table 8. Description of modules in the adolescent girl questionnaire

Module	Topic	Description	Respondent
1	Identification	School and grade of adolescent	Enumerator
2	Adolescent and family background	Age, DOB, grade level, language, characteristics of mother/father	Adolescent
3	School attendance	Attendance, reasons for absences, extracurricular activities, class performance	Adolescent
4	Exposure to nutrition information	Exposure to adolescent nutrition and/or WASH information at school and outside of school, and exposure to media and food/drink advertisements	Adolescent
5	Dietary diversity	Dietary diversity of the adolescent in the past 24 hours	Adolescent
6	Meal and snacking habits	Meals/snacks taken during school days, foods consumed before and during school, access to food vendors near school grounds	Adolescent
7	WASH practices	Handwashing, drinking water, food hygiene, menstruation	Adolescent
8	Health and health seeking behaviors	Illness, health seeking behaviors, weight and body image	Adolescent
9	Health and nutrition knowledge	General knowledge of health and nutrition, including WASH and importance of various macro and micronutrients	Adolescent
10	Home food environment	Availability of foods at home	Adolescent

11	Food security	Prevalence of household hunger using the FANTA household food insecurity access scale (HFIAS)	Adolescent
12	Parent-adolescent interactions	Relationship and interactions with parents, and perceptions of parents' monitoring of food and eating habits	Adolescent
13	Social desirability	Desire for social approval	Adolescent
14	Gender, marriage beliefs and decision-making power	Opinions about girls' and boys' education, marriage and household roles, and decision-making power in the household	Adolescent
15	Anthropometry	Weight and height measurements	Adolescent

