#### 4.1.5 Parent questionnaire

Interviews with parents of adolescent girls will be conducted at baseline and endline and gather information on school involvement, exposure to nutrition information, dietary diversity, health and nutrition knowledge, food security, home food environment, social desirability, gender and marriage beliefs and decision-making power, dwelling and assets.

Table 9. Description of modules in the adolescent girls' parents' questionnaire

Module	Topic	Description	Respondent
1	Identification	School and respondent type	Enumerator
2	Household roster	Information on composition of the household, including designation of the head of household, a list of all household members, their ages and sex, and their relationship to the adolescent girl, and the highest educational level attained and activity/employment in the past month of all household members at least 15 years of age	Parent
3	School involvement	School fees, and participation in parent-teacher association, school management committee and teacher meetings	Parent
4	Exposure to nutrition information	Exposure to adolescent nutrition and/or WASH information, and exposure to media and food/drink advertisements	Parent
5	Dietary diversity	Dietary diversity of the adolescent and household in the past 24 hours	Parent
6	Home food environment	Availability of foods at home	Parent
7	Health and nutrition knowledge	General knowledge of health and nutrition, including WASH and	Parent

		importance of various macro and micronutrients	
8	Parent-adolescent interactions	Relationship and interactions with adolescent, monitoring of food and eating habits, adolescent weight and body image	Parent
9	Social desirability	Desire for social approval	Parent
10	Gender, marriage beliefs and decision-making power	Opinions about girls' and boys' education, marriage and household roles, and decision-making power in the household	Parent
11	Food security	Prevalence of household hunger using the FANTA household food insecurity access scale (HFIAS)	Parent
12	Dwelling	House construction (materials used for floor, walls, and roof), availability of water and electricity, sources of fuel/energy for cooking, WASH facilities	Parent
13	Assets	Ownership of durable household goods (in working condition), including tools for agricultural production	Parent

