### 2.1 Research question 1 (impact on diets of adolescent girls)

For impact estimates, outcome measures related to adolescent diet will be used from the AG dataset only.

Table 2. Outcome measures for RQ1

Outcome	Indicator	Data source
Dietary diversity, consumption of unhealthy foods, and meal frequency	
Primary outcome:
 
 
- Dietary diversity score (# of food groups, out of 10 groups)
 
 
Secondary outcomes:
 
 
- % AG consumed unhealthy foods in past 24h (i.e., sweet foods and sweets, fried and salty foods, and sugar-sweetened beverages)
 
- Mean meal frequency score (# meals or snacks, out of 6 times)
 
	AG survey

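### Adverse-event recording is described only alongside delivery of the package, and the SAP names no by-arm analysis of the weight, body-image and illness data collected in both arms

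*Protocol*

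**What the plan says.** **Event recording.** Protocol 5.2 states that "we do not anticipate any harms from the study". It then says that "Any adverse events or unintended effects during provision of interventions will be recorded and monitored", with referral to a health provider where appropriate. It names no form, timing, responsible role, arm or analysis.

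**The package.** Protocol 2.3, Table 2, includes this component for intervention schools: "Trained science teachers take anthropometric measurements of adolescent girls to calculate BMI and provide nutrition counseling". The control column reads None for that row, for peer mentoring and for community gatherings. In the other rows control schools have their standard or routine activities.

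**Survey data.** Protocol 4.1.4 says "Interviews with adolescent girls will be conducted at baseline and endline". Module 8 of the girl questionnaire covers "Illness, health seeking behaviors, weight and body image" and module 15 covers "Weight and height measurements". Module 8 of the parent questionnaire (Protocol 4.1.5) includes "monitoring of food and eating habits, adolescent weight and body image". Protocol Table 3 gives 270 girls and 270 parents per arm at endline, and 81 of each per arm at baseline.

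**Analysis.** The diet outcomes in SAP 2.1 are the dietary diversity score, unhealthy food consumption and "Mean meal frequency score (# meals or snacks, out of 6 times"). BMI appears in SAP Tables 3 and 4 only as coverage or delivery of measurement and counselling. Weight, height, BMI values, body image and illness are absent from SAP Tables 2 to 6 and from the characteristics listed in SAP 3.2.

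**The concern.** The package has teachers weigh girls aged 10-14, counsel them on BMI and discourage certain foods. Protocol 2.1 reports thinness in roughly 45% of girls aged 15-19 in Somali and 17.4% in SNNPR. Weight worry, eating less or lower weight are conceivable unintended effects in that setting, though nothing in the documents shows that they occur.

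A list of events noted during delivery in one arm has no comparator, so it cannot separate effects of the package from what would have happened anyway. The randomised comparison that could help is available in the endline survey but is not planned. Protocol 2.1 says policymakers want results they can use for scale-up, so an expectation of no harm that is never examined could be carried forward. Girls are also told at consent about the COVID-19 risk of close contact for anthropometry (Protocol 6.3), yet the SAP names no use for those measurements.

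**Working it through.** The documents give no harm rate, harm sample size or precision target, so there is no stated figure to reproduce. The check has two parts.

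**1. Which sources give a between-arm contrast?**

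| Source | Control arm covered? | By-arm analysis named? |
|---|---|---|
| Events during provision (Protocol 5.2) | Not described | No |
| Height and weight (girl module 15) | Yes | No |
| Illness, weight and body image (girl module 8) | Yes | No |
| Adolescent weight and body image (parent module 8) | Yes | No |
| Meal frequency (SAP Table 2) | Yes | Yes (SAP 3.3) |
| Missed school (SAP Table 4) | Yes | Yes (SAP 3.3.1) |

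SAP 3.1 makes applicable tests two-sided so that unexpected effects can be found. The last two rows can therefore show a change in either direction.

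**2. What precision would a by-arm table have?**

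Inputs from Protocol 2.6: 270 girls per arm at endline, 10 per school, 27 schools per arm, and intra-cluster correlations of 0.015 and 0.18. Those correlations were set for the number of food groups; applying them to body-image, illness or anthropometric items is an assumption. The 10% and 30% prevalences are also assumptions.

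Design effect = 1 + (10 − 1) × ICC
- ICC 0.015: 1 + 9 × 0.015 = 1.135
- ICC 0.18: 1 + 9 × 0.18 = 2.62

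Half-width of the 95% CI for a difference in proportions = 1.96 × √(2p(1 − p) × design effect / 270). For a standardised mean it is 1.96 × √(2 × design effect / 270).

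| Quantity | ICC 0.015 | ICC 0.18 |
|---|---|---|
| p = 0.10 | 1.96 × √(0.18 × 1.135/270) = 0.054 | 1.96 × √(0.18 × 2.62/270) = 0.082 |
| p = 0.30 | 1.96 × √(0.42 × 1.135/270) = 0.082 | 1.96 × √(0.42 × 2.62/270) = 0.125 |
| Mean, SD units | 1.96 × √(2 × 1.135/270) = 0.18 | 1.96 × √(2 × 2.62/270) = 0.27 |

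For scale, the difference detectable with 80% power at two-sided 0.05 is (1.96 + 0.84) × √(2 × design effect / 270), or about 0.26 SD at ICC 0.015 and 0.39 SD at ICC 0.18.

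**The case against.** The strongest reply is that this is an education package, that the plan already looks in both directions where it matters, and that the extra table would be imprecise. Much of that stands.

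- SAP 3.3 estimates meal frequency by arm and SAP 3.1 tests it two-sided, so girls eating less often could be seen. Missed school and parental food control are compared by arm under SAP 3.3.1. None of these measures weight, body image or illness. Protocol 4.4 calls all tests one-sided, which conflicts with the SAP and needs reconciling separately; the partial cover described here relies on the SAP's version.
- SAP Section I shows that the promoted messages also include five or more food groups a day, breakfast and healthy snacks. Reduced intake is therefore not the obvious direction of effect, and the thinness figures are background prevalence in an older age group.
- Only module titles are visible. Whether the body-image items capture dissatisfaction or worry cannot be judged from the documents.
- Implementation lasted about four months (SAP 1.2), so BMI may move little.

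Some stronger readings are tempting but unsupported. A reader might infer that control schools have no harm data, but control girls and parents supply the survey items, which is why the fix works. A reader might infer that the trial cannot examine harms, but the gap is in the analysis plan and not in the data. A reader might also infer that events are collected by spontaneous report, or that the sponsor plans to declare the package safe. Section 5.2 gives no collection method and states an expectation, and Protocol 1.2 poses no safety question. Finally, meal frequency might be taken as a benefit-only outcome, but the SAP lists it neutrally as a mean score.

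**Conclusion.** The point holds as a gap in the analysis plan. The one described event record is tied to the intervention arm's activities and has no described control-arm counterpart. The two-arm survey data that could fill the gap have no named by-arm analysis. Existing two-sided comparisons of meal frequency and missed school cover part of it.

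A by-arm table would give 95% half-widths of about 5 to 8 points at 10% prevalence, 8 to 12.5 points at 30%, and 0.18 to 0.27 SD. These rest on full endline recruitment, complete items, the dietary correlations carrying over, and the assumed prevalences. The table could exclude only fairly large effects, and a null result must not be reported as evidence of safety. It is still worth making, because the plan as written produces no estimate for these outcomes.

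**What to change.** 1. Add one unintended-effects table to SAP 3.3, using the same endline regression with school-clustered standard errors. Include BMI-for-age z-score or thinness (naming the growth reference; girl module 2 supplies age and date of birth), the module 8 weight and body-image items, and the module 8 illness items. Cross-refer to meal frequency and state that it is read in both directions.
2. Report arm differences with 95% CIs and no significance claims, and say that the table cannot establish safety.
3. In Protocol 5.2, state that events recorded during provision come from the intervention arm and that the between-arm comparison comes from the endline survey.
4. Fix the item definitions before looking at results by arm, or label the table post hoc. SAP 1.2 describes the endline survey in the past tense, so parallel event recording in control schools may no longer be possible.

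The cost is some SAP and protocol wording and one table, with no new data collection. The downside is a few more descriptive comparisons with wide intervals.

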### 5.3 Auditing

Not applicable.

## VI. Ethics and Dissemination

### 6.1 Research ethics approval

This protocol, informed consent forms, and study questionnaires will be submitted for ethical clearance from the Institutional Review Boards (IRB) of FHI 360 and the International Food Policy Research Institute in Washington, DC. In Ethiopia, ethical clearance will be obtained from the Addis Continental Institute of Public Health IRB.

A COVID-19 country risk assessment system was developed by IFPRI to help researchers and IFPRI's IRB assess COVID-19 risk in countries where fieldwork is planned. In function of the level of COVID-19 risk identified in country, data collection methods will be adapted to minimize the transmission risk of COVID-19. Justification for resuming fieldwork with in-person contacts will be provided and accepted by the IRB.

### 6.2 Protocol amendments

All amendments to the protocol will be reported (by IFPRI Co-Investigators and ACIPH Co-Investigator) to and agreed upon with Alive & Thrive. Substantive changes to the protocol that may impact the safety of participants or the scientific validity, scope, or ethical rigor of the study will be reviewed by the IFPRI IRB.

Version control using protocol version identifiers and dates will be used to track the history of amendments and identify the most recent protocol version.

### 6.3 Consent or assent

After explaining the study's objectives and procedures, enumerators will seek and obtain written informed consent from eligible study participants and the parent/guardian of the participant. Participation in the study is completely voluntary. Participants are free to withdraw at any time by informing survey or program staff.

All COVID-19 transmission risks to study participants (including close contact required for taking anthropometric measurements) and the precautionary measures that will be followed during data collection to limit the risk of transmission will be included in the informed consent.

### 6.4 Confidentiality

Immediately after data collection, all data will be uploaded and stored securely in an IFPRI-server-based Dropbox Professional folder. To protect respondent confidentiality, only senior IFPRI researchers will have access to data and documents containing personally identifiable information. Research support staff and other project team members will have access to depersonalized data—located in a separate IFPRI-server-based Dropbox Professional folder—where direct identifiers have been replaced by randomly generated numeric IDs.

Data that is made publicly available will be carefully screened to remove any indirect and geographic identifiers which may breach the confidentiality of respondents.

### 6.5 Declaration of interests

The authors declare that they have no competing interests.

## 6.6 Access to data

All Co- and Principal Investigators of the project (based in the US and in Ethiopia) will have full access to the cleaned data. Other project team members will have access to data that has had all personally identifiable information removed.

In compliance with donor (Bill & Melinda Gates Foundation) open access policy requirements, fully anonymized datasets will be made publicly available one year after the end of the project. Metadata and other documentation of data collection procedures (such as the codebook, data collection instruments and interviewer guides/protocols) will also be made publicly available.

## 6.7 Ancillary and post-trial care

Not applicable.

## 6.8 Dissemination policy

Close engagement with the government of Ethiopia is of primary importance to the project. The A&T Ethiopia team will be working in close partnership with government entities on strengthening nutrition education in schools at the national and regional levels throughout the duration of the project. Findings will be disseminated through in-country events, presentations, and conferences.

Within the research community, we aim to have the research results peer-reviewed and published in high quality journals. Preliminary research findings may be presented at international conferences and internal IFPRI seminars.

## VII. Timeline

### 7.1 Study timeline

Deliverable/Activities	2019											
	Jan	Feb	Mar	Apr	May	Jun	Jul	Aug	Sep	Oct	Nov	Dec
1. Study protocol												
Discuss study and evaluation design with A&T	x	x	x									
Prepare study protocol			x	x	x	x						
2. Baseline data collection tools												
Develop questionnaires/data collection tools				x	x	x						
Select and contract survey firm						x	x					
Translate questionnaire							x					
Program CAPI questionnaire							x	x				
3. Local and US-based IRB approvals												
IRB application at IFPRI								x				
IRB application in Ethiopia							x					
4. Baseline survey implementation												
Pretest, revise and finalize questionnaire								x				
Enumerator training									x			
Data collection										x	x	
5. Data cleaning and analyses												
Data cleaning											x	x
Data analyses												x

Deliverable/Activities	2020											
	Jan	Feb	Mar	Apr	May	Jun	Jul	Aug	Sep	Oct	Nov	Dec
Data analyses	x											
6. Baseline results tables and datasets												
Draft and finalize baseline results	x	x										
Prepare clean datasets			x									

Deliverable/Activities	2021											
	Jan	Feb	Mar	Apr	May	Jun	Jul	Aug	Sep	Oct	Nov	Dec
7. Endline data collection tools												
Develop questionnaires/data collection tools	x	x										
Translate questionnaire		x										
Program CAPI questionnaire		x	x									
8. Local and US-based IRB approvals												
Obtain IFPRI IRB approvals to conduct fieldwork			x									
Obtain local IRB approvals to conduct fieldwork			x									
9. Endline survey implementation												
Pretest, revise and finalize questionnaire			x									
Enumerator training			x									
Data collection			x	x								
10. Data cleaning and analyses												
Data cleaning					x	x						
Data analyses						x	x	x	x	x		
11. Endline results tables and datasets												
Draft endline results							x	x				
Finalize endline report and findings								x	x			
Prepare clean datasets										x		

**I. Study Background and Approach**

In Ethiopia, Alive & Thrive (A&T) has developed a package of adolescent nutrition interventions implemented through school-based and community platforms. Interventions are implemented in one-half of the 54 primary schools across two regions – SNNP (31 schools) and Somali (23 schools). Core interventions include: (1) classroom lessons about adolescent nutrition and healthy diets, (2) flag ceremonies/ assemblies to remind about key healthy eating messages, (3) adolescent girls club/student peer mentoring on adolescent nutrition, and (4) parent-teacher meetings to educate parents about adolescent nutrition and healthy diets. Other interventions include body mass index (BMI) measurement and counseling for adolescent girls, home visits by health extension workers (HEW) to advise parents of adolescent girls, and community gatherings to build awareness about adolescent nutrition. The key behaviors promoted by these interventions were dietary diversity (at least 5 food groups daily, with locally available foods), eating breakfast before school and healthy snacks daily, and avoiding unhealthy/junk foods.

